3.2.2 Hypotheses to be investigated

To assess the effects of mepolizumab on health status, well-being, exercise capacity, frailty, moderate exacerbations, healthcare usage and death compared with placebo in patients admitted to hospital with an eosinophilic exacerbation of COPD.

3.3 Exploratory Samples for future research (optional)

Details regarding the definition and analysis of Biomarkers, Muscle Wasting, Immunophenotyping and Microbiology outcomes measured at Weeks 0, 4, 8, 12, 24, 36 and 48 (Participants consented to the truncated follow-up will receive minimum 24 weeks follow-up), respectively, are not included in this SAP as the analysis will not be carried out by the LCTU.

3.4 Subgroups and/or interactions

Subgroup analyses of the primary outcome will be carried out on the stratification factors. These are baseline MRC dyspnoea score (≤ 3 , > 3) and past hospitalisation in the previous 12 months (0 , ≥ 1) and WHO clinical progression score at baseline (4, 5, 6). A stratified Cox model will be fitted to allow the form of the underlying hazard function to vary across the levels of prognostic variables.

3.5 Other variables to be summarised

Other remaining variables of the trial will be summarized by treatment group and overall.

4 Analysis Sets/Populations

4.1 Protocol deviations

4.1.1 Major deviations

All doses of mepolizumab/placebo will be administered subcutaneously (SC) at the Respiratory BRC by an unblinded member of the study team. The prescribed dosage and mode of administration (see section 8.4 for dosage schedules) must not be altered. Injection time will be documented in the CRF. Any changes from the intended regimen must be recorded in the CRF.

Participants will be allowed to miss one dose of the study drug only, or they will be discontinued from the trial treatment.

- Participant found to be Ineligible for the trial, randomized in error.
- Non-compliance with the randomised treatment:
 - Modification of the prescribed dosage during the Trial.
 - Change in the form of IMP before administration of mepolizumab or placebo according to the active protocol version.
- Receiving wrong treatment as per randomised allocation.
- Receiving non-permitted treatment during the Trial (i.e. participants with pre-existing helminth infections who should have been treated before taking part in the Trial, as stated in the Protocol).
- Missing more than one dose of the study drug whilst on treatment. The trial team identifies participants that have missed two doses of the study drug whilst on treatment and determines that treatment should be discontinued and give the reason for discontinuation of treatment in the end of treatment CRF as being due to non-compliance. Only participants with a discontinuation reason of non-compliance are deemed a major protocol deviation.

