8.4 Dosage and excipients

Dosing will be undertaken every four weeks (+/- 7 days) over 48 weeks (12 doses in total), each consisting of 100mg of mepolizumab or placebo, administered subcutaneously. Participants are required to complete the scheduled clinic visits within the specified time windows in order to maintain sufficient intervals between doses. Trial medication can only be administered at the Respiratory BRC. The participant will return on an outpatient basis following their initial hospitalisation every four weeks to receive their scheduled dose and undertake trial assessments. For participants who do not receive dosing during their index hospitalisation, the first injection must occur within seven days of discharge. The participant's time in the trial begins at randomisation.

Scheduled doses can be delayed by up to four weeks. The exception will be if dosing is delayed due to an exacerbation resulting in hospitalisation, where there will be no limit on the length of delay, and the next dose will be administered at the next due date or as soon as possible afterwards to allow the participant to recover. A delay will then be carried through to all their subsequent study visits. If the participant misses a dose, it will be recorded in the medical notes and the next scheduled dose will be administered. Participants will be allowed to miss one dose of the study drug only, or they will be discontinued from the trial treatment. Dosing completed outside of the seven-day window will be recorded as a protocol deviation.

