4.1.2 Minor deviations

Participants visit/assessment not performed as per protocol

4.2 *Intention-to-treat Population*

The primary analysis for each efficacy outcome will be by ‘intention to treat’ analysis; all the participants randomised into the trial (regardless of whether they received trial drug) will be analysed in their allocated group. Outcome data obtained from all participants will be included in the data analysis.

4.3 *Modified intention-to-treat population*

The modified intention-to-treat will be comprised all the participants randomised to the trial (regardless of whether they received trial drug), analysed in their allocated group, where data is available. Therefore, participants with missing outcome data will be excluded from the analysis (i.e complete case analysis). No imputation will be carried out for the missing data.

4.4 *Per-protocol Population*

The per protocol population will contain all participants randomised who do not reach any of the listed definitions for major protocol deviations. Individuals without a major deviation will be included in the per-protocol population whilst on trial treatment, this is considered to be 4 weeks after the last dose. If a participant dies before ending trial treatment, time is capped by death date.

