6.4.2 Secondary Analyses of Primary Outcomes

The secondary analysis of the primary outcome will take place on a subset of participants defined by the per-protocol population with individuals being censored at the earliest of end of their trial treatment (4 weeks after last dose) or last follow-up. The analysis will otherwise match the approach described above for the primary analysis.

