9.1 Appendix 1: Templates for Tables, Listings and Figures

Table1: Disposition of Patients by treatment arm

	Control, n (%)	Mepolizumab, n (%)	Total, n (%)
Randomised patients			
Completed trial follow-up (End of trial assessment)			
Discontinued due to			
Lost to follow-up			
Withdrawn			
Deaths			
Remained on treatment for intended follow-up period			
Discontinued treatment early			
Reasons:			
Participant decision			
Adverse Event			
Unable to Tolerate Drug			
Participant non-compliance			
Lost to Follow up			
Investigator decision			
Participant Ineligible			
Withdrawn due to Medical Reasons			
Death			
Number of doses received			
1			
2			
3			
4			
5			
6			
7			
8			
9			
10			
11			
12			

Figure 1: A Swimmer plot of participants' discontinuation from the trial with reasons

Table 1: Case Report Form (CRF) return

CRF	Placebo Returned/Expected (%)	Mepolizumab
Visit 1 (Week 0)	Follow-up due	
	Follow-up completed	
Visit 2 (Week 4)	Follow-up due ^a	
	Follow-up completed	
Visit 3 (Week 8)	Follow-up due ^a	
	Follow-up completed	
Visit 4 (Week 12)	Follow-up due ^a	
	Follow-up completed	
Visit 5 (Week 16)	Follow-up due ^a	
	Follow-up completed	
Visit 6 (Week 20)	Follow-up due ^a	
	Follow-up completed	
Visit 7 (Week 24)	Follow-up due ^a	
	Follow-up completed	
Visit 8 (Week 28)	Follow-up due ^a	
	Follow-up completed	
Visit 9 (Week 32)	Follow-up due ^a	
	Follow-up completed	
Visit 10 (Week 36)	Follow-up due ^a	
	Follow-up completed	
Visit 11 (Week 40)	Follow-up due ^a	
	Follow-up completed	
Visit 12 (Week 44)	Follow-up due ^a	
	Follow-up completed	
Visit 13 (Week 48)	Follow-up due ^a	
	Follow-up completed	

^a Will be defined as participants who have passed the visit window stated in the Protocol.

Table 2: Demographic and Baseline Clinical Characteristics

Characteristics	Descriptive	Placebo (n=)	Mepolizumab (n=)	Total (n=)
Age	N			
	Mean [SD]			
	Median [IQR]			
	Min, Max			
Gender	Male			
	Female			

Ethnicity	White
	Asian or Asian British
Smoking status	Current Smoker
	Ex-Smoker
BMI	N
	Mean [SD]
	Median [IQR]
	Min, Max
Number of cigarettes per day	N
	Mean [SD]
	Median [IQR]
	Min, Max
Number of years smoked	N
	Mean [SD]
	Median [IQR]
	Min, Max
Number of emergency admissions (all cause) in previous 12 months	N
	Mean [SD]
	Median [IQR]
	Min, Max
Number of courses of steroids without antibiotics for your chest (COPD exacerbations) in previous 12 months	N
	Mean [SD]
	Median [IQR]

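### Per-protocol analyses: after two missed doses, a stop reason entered later decides whether a participant is removed from day 0 or kept until 4 weeks after the last dose

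*SAP*

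**What the plan says.** **Who is excluded.** SAP 4.1.1 sets the allowance: "Participants will be allowed to miss one dose of the study drug only". Missing more is a major deviation, but the same bullet has the trial team identify the participant, decide that treatment should stop, and "give the reason for discontinuation of treatment in the end of treatment CRF as being due to non-compliance". It then adds: "Only participants with a discontinuation reason of non-compliance are deemed a major protocol deviation". The disposition table in SAP Appendix 1 lists other stop reasons beside participant non-compliance, among them "Participant decision", investigator decision, adverse event and medical reasons. No rule separates them.

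**How long the others count.** SAP 4.4 says: "Individuals without a major deviation will be included in the per-protocol population whilst on trial treatment", with treatment taken to end 4 weeks after the last dose. SAP 6.4.2 applies this to the primary outcome, with "individuals being censored at the earliest of end of their trial treatment (4 weeks after last dose) or last follow-up". SAP 6.5.2 uses the same clock for the offset of the two count outcomes.

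**What dosing may look like.** Protocol 8.4 sets a four-weekly schedule with a 7-day window and adds: "Scheduled doses can be delayed by up to four weeks". One dose may be missed, and delay after a hospitalised exacerbation has no limit.

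**A different definition elsewhere.** Protocol 10.3.3 and 10.7 define per protocol, for the two count outcomes, as at least 24 weeks of trial treatment. SAP 6.8 records no changes to the planned analysis.

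**The concern.** Both rules use information that arises after follow-up has begun, and sometimes after the event itself.

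The stop reason is entered once the misses have happened and possibly once a readmission is known. If the entry is non-compliance, everything the participant contributed is dropped back to randomisation, including time and events that were on treatment under any definition. Readmission is the endpoint and can also influence whether someone goes on attending, so this removal may be related to outcome.

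The last dose can be identified only in retrospect. Whether an event in a dosing gap counts therefore depends on whether another dose follows it.

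At stake is how the only other planned analysis of the primary outcome can be read: SAP 6.4.3 plans no sensitivity analysis for it. The per-protocol rate ratios for readmissions and moderate exacerbations are affected in the same way.

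**Working it through.** **1. The plan's own figure.** Inputs from Protocol 10.1: 65% control events by 48 weeks, hazard ratio 0.6, power 0.8, alpha 0.05 (taken as two-sided).
- Freedman events: (1.960 + 0.842)² × (1.6/0.4)² = 7.85 × 16 = 125.6, so 126.
- Mepolizumab event proportion: 1 − 0.35^0.6 = 46.7%. Average of the arms: 55.9%.
- 126/0.5587 = 225.5, so 226; 226/0.95 = 237.9, so 238. The stated figures are reproduced, and nothing below changes them.
- Expected events among 238: 238 × 0.5587 = 133.

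**2. Stop reason: one dosing record, two results.**

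| | Doses given | Doses missed | Stop reason | Per-protocol contribution |
|---|---|---|---|---|
| A | weeks 0, 4, 8 | weeks 12, 16 | participant decision | weeks 0 to 12 |
| B | weeks 0, 4, 8 | weeks 12, 16 | non-compliance | none |

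A readmission at week 6 counts for A and disappears for B.

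**3. Last-dose clock.** C and D are both dosed at week 0, miss week 4 and are readmitted at week 6. If C is dosed at week 8, the event counts. If D is never dosed again, D is censored event-free at week 4. The records match only up to the event. No dose can follow a death, so a death beyond day 28 after a dose can never count.

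At the plan's control hazard, −ln(0.35)/336 per day, the chance of an event in a 28-day gap is 1 − 0.35^(28/336) = 8.4% on placebo and 5.1% on mepolizumab. In a 7-day gap it is 2.2% and 1.3%.

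**4. Size of the stop-reason rule (assumed coding rates).** Suppose a share *a* of participants with an event, and 5% of those without, are later coded non-compliance. With *a* between 10% and 20%, 13 to 27 of the 133 events are removed.

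Per participant, with constant hazards of 0.02187 per week (placebo) and 0.01312 (mepolizumab):
- Placebo: D = 0.650; time in those with an event 12.92 weeks; time in those without 0.35 × 48 = 16.80.
- Mepolizumab: D = 0.467; 10.05 and 25.57 weeks.
- Event rate after exclusion = (1 − *a*)D / [(1 − *a*) × time with event + 0.95 × time without].

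| *a*, placebo | *a*, mepolizumab | Placebo rate | Mepolizumab rate | Ratio |
|---|---|---|---|---|
| 5% | 5% | 0.02187 | 0.01312 | 0.600 |
| 10% | 10% | 0.02121 | 0.01262 | 0.595 |
| 20% | 20% | 0.01978 | 0.01157 | 0.585 |
| 10% | 20% | 0.02121 | 0.01157 | 0.545 |
| 20% | 10% | 0.01978 | 0.01262 | 0.638 |

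A Cox fit to data simulated on these assumptions agrees to within about 0.003. Equal coding moves the ratio by 0.005 to 0.015; a 10-point difference moves it by 0.038 to 0.055.

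A second set of assumptions, with a true ratio of 1, 10% of participants missing two doses and twice the hazard in that group, gives 0.98 when 30% of them in the placebo arm and 70% in the mepolizumab arm are labelled non-compliance. The extremes of 0% against 100% give 0.94 and 1.06.

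**5. Size of the last-dose clock (simulated, assumed).** With a true ratio of 1, a 2% to 10% chance of a skipped dose per visit and at most one skip, the estimate stays at about 1.00 when resumption after a gap event is equal by arm. It lies between 0.98 and 1.02 when resumption differs (for example 70% against 40%). If dosing never resumes after a gap event, about 1 to 4 events per 113 placebo participants are dropped.

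**The case against.** **Blinding.** Protocol 7.4 keeps investigators blind, so coding need not favour an arm, and with equal coding the estimate barely moves. This stands as a limit on size. It is not complete protection: Protocol section 2 says mepolizumab lowers eosinophil counts, full blood counts are scheduled at every visit, Protocol 7.9 has the results stored in the CRF, and neither document describes masking them. Differential coding is possible but not shown.

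**Separating reasons is legitimate.** Doses missed because of a hospitalised exacerbation are not non-compliance, and someone who has chosen to stop is arguably no longer missing doses while on treatment. That is fair. The gap is that no objective rule draws the line and that exclusion reaches back to day 0.

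**The 28-day window has a basis.** Protocol 9.2 uses the same 28 days as the withdrawal period. This stands. The weakness is that the window is applied after the last dose only, and lengthening it would merely move the look-ahead to a later day.

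**Stronger readings that the documents do not support.**
- A reader might infer that someone who misses several doses and is never discontinued stays in throughout. Protocol 7.8 and 8.4 require discontinuation after more than one missed dose, so that case would itself be a protocol breach.
- A reader might infer that delays over 4 weeks escape because they are not on the deviation list. Protocol 7.8 makes them a stopping trigger, hospitalised exacerbation excepted, so those participants are already censored 4 weeks after the last dose.
- A reader might infer that many deaths are lost, by applying the share of a stretched interval beyond day 28 (7/35 to 28/56) to all 14 deaths without readmission (6% × 238). That treats every interval as stretched to its maximum. If each participant had one 56-day interval, 14.28 × 28/336 = 1.2 deaths would fall in the gap.

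**Conclusion.** The point holds for the per-protocol analyses in SAP 6.4.2 and 6.5.2 and nowhere else. The stop-reason rule is the main defect: it selects on an undefined entry made after randomisation and discards valid on-treatment events. The look-ahead in the last-dose clock is real but smaller.

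Bias is negligible, a shift of about 0.01 in the hazard ratio, if coding and resumption of dosing are alike in both arms. It reaches about 0.04 to 0.05 only under an assumed 10-point difference between arms in coding after an event. The coding, skipping and resumption rates are all assumptions; the documents give none. A reader might infer that the trial's main result is at risk. It is not: the primary analysis is ITT with all randomised participants. This is a cheap improvement that makes the per-protocol result interpretable.

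**What to change.** In SAP 4.1.1 and 4.4:
- Define the missed-dose deviation from recorded dose dates, whatever the CRF reason code, and use recorded hospitalisation dates to apply the protocol's exception. SAP 5.1 already derives dose counts and intervals; hospitalisation dates are collected for the primary outcome.
- Keep these participants and censor them on the date the deviation occurs. Treat other post-baseline deviations, such as a later wrong-product dose, the same way. Exclude from day 0 only for facts fixed at baseline or for participants never dosed.
- Keep the 28-day on-treatment window, or state another number of days, and apply it to every dosing gap in every participant whether or not dosing resumes. Say how time after resumption is handled, since a dose given late but within the visit window can fall 35 days after the previous one.

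In SAP 6.5.2, use the same clock for both the counted events and the offset.

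Reconcile SAP 4.4 with the 24-week definition in Protocol 10.3.3 and 10.7, and record the change in SAP 6.8.

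The cost is SAP wording and no new data. The downside is slightly fewer events and less person-time from participants with dosing gaps.

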4.1.2 Minor deviations

Participants visit/assessment not performed as per protocol

4.2 *Intention-to-treat Population*

The primary analysis for each efficacy outcome will be by ‘intention to treat’ analysis; all the participants randomised into the trial (regardless of whether they received trial drug) will be analysed in their allocated group. Outcome data obtained from all participants will be included in the data analysis.

4.3 *Modified intention-to-treat population*

The modified intention-to-treat will be comprised all the participants randomised to the trial (regardless of whether they received trial drug), analysed in their allocated group, where data is available. Therefore, participants with missing outcome data will be excluded from the analysis (i.e complete case analysis). No imputation will be carried out for the missing data.

4.4 *Per-protocol Population*

The per protocol population will contain all participants randomised who do not reach any of the listed definitions for major protocol deviations. Individuals without a major deviation will be included in the per-protocol population whilst on trial treatment, this is considered to be 4 weeks after the last dose. If a participant dies before ending trial treatment, time is capped by death date.

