10.3.3 Secondary outcome analysis

All secondary end-points will be analysed using the ITT population, with the exception of adverse events, for which we will analyse the safety population, consisting of all participants who received at least one dose of trial medication. The count outcomes, number of hospital readmissions and number of moderate exacerbations over 48 weeks, will be analysed using the per protocol (PP) population where patients will be included in the analysis if they have a received a minimum duration of trial treatment of 24 weeks.

All time to event secondary outcomes will be analysed the same way as the primary outcome.

All count secondary outcomes, number of hospital readmissions and number of moderate exacerbations, will be analysed using a negative binomial regression model. If there is no evidence of over-dispersion, a Poisson regression model will be used in place.

All binary secondary outcomes will be compared between treatment groups using logistic regression.

All continuous longitudinal outcomes (repeated measurements) will be compared using mixed effects model with patient as a random effect to account for repeated measures over time. This method will enable handling of missing data within the follow-up visits.

This trial has a single primary outcome, therefore there will not be a formal adjustment for multiple significance testing.

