10.7 Participant population

The primary analysis for each efficacy outcome will be by 'intention to treat' analysis; all the participants randomised in to the trial (regardless of whether they received trial drug) will be analysed in their allocated group. Outcome data obtained from all participants will be included in the data analysis. The primary analysis of safety outcomes will be analysed using the safety population. The safety population will be comprised of the all individuals that received at least one injection of either the active dose or the placebo, with individuals that received any injections of the active dose being in the mepolizumab arm.

Some of the secondary outcomes i.e. number of hospital readmissions and number of moderate exacerbations over 48 weeks, will be analysed on the per-protocol population where patients will be included in the analysis if they have a received a minimum duration of trial treatment of 24 weeks.

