6.5 Secondary Outcome Analyses

6.5.1 Primary Analysis of Secondary Outcomes

All secondary outcome (except for AEs and SAEs) will be analysed on the modified intention to treat population. The secondary outcomes of adverse and serious adverse event counts will be analysed on the safety population.

All time to event secondary outcomes will be analysed the same way as the primary outcome.

All count secondary outcomes, number of hospital readmissions and number of moderate exacerbations, will be analysed using a negative binomial regression model. If there is no evidence of over-dispersion, a Poisson regression model will be used in place.

All continuous longitudinal outcomes (repeated measurements) will be compared using mixed effects model with patient as a random effect to account for repeated measures over time. This method will enable handling of missing data within the follow-up visits.

This trial has a single primary outcome, therefore there will not be a formal adjustment for multiple significance testing.

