6.5.1.2 Continuous Longitudinal Outcomes

All continuous longitudinal outcomes (repeated measurements) will be compared using mixed effects model with explanatory variables of treatment arm, stratification variables, visit number in weeks (categorical) and baseline value as fixed effects with participant identification as a random effect to account for repeated measures over time. This method will be able to handle missing data during the follow-up measurements. Adjusted mean differences alongside two sided 95% CI and P-value will be reported for these outcomes. Mean and standard deviation at baseline and over 48 weeks of the observed data will be presented by treatment arm. The adjusted mean change from baseline in each arm (with 95% confidence intervals) and the adjusted mean difference between groups (with 95% confidence intervals) will be presented alongside the 2-sided p-value from the model.

The model residuals corresponding to the continuous longitudinal outcomes will be assessed for normality by performing the Shapiro-Wilk Test.

Data will be assessed for the normality assumption using visualisation, taking into account sample size for each variable, the nature of potential outliers, and similarity between mean and median values (recognising formal statistics to test for normality

often lead to spurious results). If the distribution of the variable is found to be far from normally distributed, a log transformation will be used to modify the non-normality. In these cases adjusted geometric mean on the original scale (i.e. after anti-logging the result on the log scale) alongside standard errors on the log scale will be presented of the observed data. Geometric mean ratios from the model (with associated 95% CI and 2-sided p-value) will be reported to compare treatment groups.

Should a log transformation not correct for non-normally distributed data a non-parametric test such as the Mann Whitney U test can be utilised to assess the distribution of ranks between the treatment arms. Adjustment for other variables in the model including baseline value will not be possible and the Median (inter-quartile range), minimum, maximum of the observed data in each treatment arm will be presented along side the 2-sided p-value.

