6.5.1.3 Count Outcomes

A generalised linear model (assuming a negative binomial distribution, which accounts for variability among participants in the number of and frequency of the count variable) will be fitted for each count outcome measure with explanatory variables of treatment arm and stratification variables, and log-time on study as an offset. The offset (log-time), allows for different lengths of follow-up time for each participant (Keene et al, 2008). Time on study will be capped at 49 weeks. This assumes that missing data is missing at random (MAR), and will be applied where all of the available observed data are analysed without deletion nor imputation.

The count data is assumed to follow a negative binomial distribution with the over dispersion. If the dispersion is found to be non-significant (i.e no evidence of over-dispersion) we will consider the simpler Poisson model where the dispersion parameter equals to zero. The ratio of the rates (RR) on the intervention arm relative to placebo, associated two-sided 95% confidence interval (CI) and p-value will be reported. A value of 1.0 would indicate the same rate as placebo; the lower the ratio the greater reduction in exacerbations compared with placebo. A two-sided p-value ≤ 0.05 will be considered

as a significant difference in the number of COPD exacerbations in 48 weeks between the two treatment arms.

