6.5.3 Sensitivity Analyses

The primary analyses for all none time event outcomes (i.e continuous, binary and count outcomes) will consider any missing data to be missing at random (MAR) and complete case analysis carried out. However, if comparison of patterns of missingness and descriptive differences between treatment arms indicate this assumption is not valid, additional sensitivity analyses may be carried out and methods of imputation will be included in detail in the statistical analysis plan.

To ensure the reliability of the analysis of key secondary outcome measures, we will conduct a sensitivity analysis under various scenarios. This will involve evaluating the secondary outcomes; number of readmissions, number of exacerbations, and SGRQ (assessed for three sub-domains and the total score), to thoroughly assess the robustness of our results.

Individuals will be considered to have had some missing data for the two count variables if they have less than 47 weeks (48 weeks – 7day window) follow-up with the exception of those with planned truncated follow-up.

In the first approach, regardless of whether missingness is assumed to be random or non-random, we will perform the outlined statistical procedures. Additionally, we will provide descriptive characteristics of the missing group compared to the non-missing group, exploring potential similarities or dissimilarities between them. This comprehensive approach allows for a thorough examination of the impact of missing data on our study outcomes.

In the second approach, we are aware that throughout the trial, some participants may leave the study due to a high number of exacerbations or death before reaching their 48-week follow-up. This leads to missing data that is not at random, rendering

standard imputation methods inappropriate. Therefore, the data for key secondary outcomes for these participants will be analysed in the following way:

Pattern Mixture Model:

Robustness of the results will be assessed within the pattern mixture model. A pattern mixture model is a type of statistical model used to analyse data with missing values, especially when the missingness is not at random (MNAR).

This method is a 2-stage procedure where the 1st stage involves the use of multiple imputation to impute all missing values assuming data are “missing at random”.

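### For the longitudinal secondary outcomes, the SAP and protocol state both a complete-case rule and a mixed model on all observed visits; one rule has to be chosen

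*SAP*

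**What the plan says.** Complete case:

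- SAP 6.5.1 assigns the analysis set: "All secondary outcome (except for AEs and SAEs) will be analysed on the modified intention to treat population".
- SAP 4.3 defines that set. It starts from everyone randomised, in the allocated arm and subject to data being available, and then adds that "participants with missing outcome data will be excluded from the analysis (i.e complete case analysis", with no imputation.
- SAP 6.5.3 says the primary analyses of the continuous, binary and count outcomes "will consider any missing data to be missing at random (MAR) and complete case analysis carried out". Protocol 10.8 has the same rule.

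All observed data:

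- SAP 6.5.1, like Protocol 10.3.3, specifies a mixed model with a patient random effect and gives the reason: "This method will enable handling of missing data within the follow-up visits". SAP 6.5.1.2, which sets out the model, repeats it: "This method will be able to handle missing data during the follow-up measurements". For ordinal eMRC, SAP 6.5.1.4 carries the same approach over with a logit link.
- Protocol 10.3.3 says "All secondary end-points will be analysed using the ITT population", adverse events excepted. Protocol 10.7 says "Outcome data obtained from all participants will be included in the data analysis", and SAP 4.2 has the same sentence.

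SAP 6.8 records no change to the planned analysis.

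**The concern.** A participant with SGRQ at weeks 4, 8 and 12 who then stops attending contributes three visits under the mixed-model text and none under the complete-case text. Two statisticians following this SAP could therefore report different samples and different estimates. Complete case is also not generally valid under the MAR assumption stated in the same sentence of SAP 6.5.3, whereas a likelihood-based mixed model on all observed visits is.

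The plan makes incomplete records likely:

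- After stopping treatment, a participant need only agree to collection of admissions and deaths (Protocol 7.8).
- Those lost to follow-up are traced through hospital records for exacerbations, hospitalisations and death (Protocol 7.11), which yields no questionnaires or physical measures.
- Only spontaneous sputum is collected (Protocol 7.7.5), and failure to produce a sample is not a deviation (Protocol 13.5).
- The protocol cites 12% mortality after severe exacerbations (Sections 1 and 9.4).
- Truncated participants do not have every scheduled assessment.

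**Working it through.** **1. The base of 238.** The plan gives no sample size or missing-data rate for these outcomes. Its primary-outcome figure reproduces by Freedman's formula. Events = (1.96 + 0.8416)² × [(1 + 0.6)/(1 − 0.6)]² = 7.849 × 16 = 125.6, so 126. Mean event probability = [0.65 + (1 − 0.35^0.6)]/2 = (0.65 + 0.467)/2 = 0.559. Then 126/0.559 gives 226, and 226/0.95 gives 238. The 5% covers only participants who never receive a first dose.

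**2. Who cannot be complete by design.** Assessments fall at weeks 4, 8, 12, 24, 36 and 48 after baseline. Under SAP 2.1, July to December 2023 entrants finish at weeks 44, 40, 36, 32, 28 and 24. The SAP does not say which model visit their early Final Follow-up belongs to.

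- If it fills the week-48 slot, July and August entrants can be complete. September to December entrants lack a separate week-36 assessment, and December entrants also lack a separate week-24 one.
- If it does not, all six months are incomplete.

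Even accrual is 238/36 = 6.6 a month. Protocol 10.2 gives 13 a month, which is usable only as an upper bound because 13 × 36 = 468.

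| Final Follow-up fills week 48? | Months affected | At 6.6 a month | At 13 a month |
|---|---|---|---|
| Yes | 4 | 26.4 (11%) | 52 (22%) |
| No | 6 | 39.7 (17%) | 78 (33%) |

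**3. Effect on the estimate.** Simulation of 1,500 trials per scenario, 238 randomised, 1:1, six post-baseline visits. A random-intercept REML model with arm, categorical visit and baseline was fitted to all observed visits, then only to participants with every visit. Assumed, not in the documents: true difference −4, between-patient SD 14, within-patient SD 11. Dropout from the second visit onwards has log-odds −3.1 + 0.06 × (previous score − 50), giving about 23% to 25% overall. In the arm-differential scenario the score term acts in the placebo arm only. Truncated participants count as incomplete.

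| Scenario | All observed visits: estimate (SE) | Complete case: estimate (SE) | Complete-case n |
|---|---|---|---|
| 17% truncated, no dropout | −3.89 (1.27) | −3.90 (1.39) | 198 |
| 33% truncated, no dropout | −4.03 (1.28) | −4.02 (1.55) | 159 |
| Dropout, same mechanism in both arms | −3.99 (1.31) | −3.71 (1.41) | 179 |
| Same, plus 17% truncated | −4.00 (1.32) | −3.72 (1.55) | 149 |
| Dropout tied to scores on placebo only | −4.04 (1.30) | −2.48 (1.43) | 182 |

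The Monte Carlo error of each mean is 0.03 to 0.04.

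- Precision lost to truncation alone: 1.39/1.27 = 1.09 and 1.55/1.28 = 1.21. For the 11% case, √(238/211.6) = 1.06.
- Bias with the same mechanism in both arms: (4 − 3.71)/4 = 7%.
- Bias with the arm-differential mechanism: (4 − 2.48)/4 = 38%.

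**The case against.** **A harmonising reading exists.** SAP 4.3 includes everyone randomised for whom data are available, and SAP 6.5.1.2 fits visit as a category in a repeated-measures model. An every-visit rule would defeat that model's purpose. The authors may have meant only that participants with no outcome data drop out and nothing is imputed. That is plausible as intent. But the next sentence of SAP 4.3 excludes participants, not visits, and labels this complete case. The explicit opposite statement in SAP 6.5.1.3, "will be applied where all of the available observed data are analysed without deletion nor imputation", covers only the counts.

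**An unscheduled visit need not be missing.** The CRF-return table in SAP Appendix 1 counts a visit as due only once its window has passed, and SAP 6.5.3 exempts planned truncation for the two count outcomes. The truncation counts are therefore conditional. No such exemption is written for the longitudinal outcomes.

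**Checks already exist.** SAP 6.5.3 plans multiple imputation (50 imputations) and pattern-mixture analyses for SGRQ total and sub-domains. This stands for SGRQ. The other longitudinal outcomes have no such check.

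**Stronger readings that the documents do not support.** A reader might infer that the SAP brought complete case into an all-data protocol. It did not: Protocol 10.8 carries the same rule, so the conflict is inside the protocol too. A reader might also infer that SAP 6.5.3 expects dropout that depends on scores and differs by arm. It says only that some participants may leave because of many exacerbations or death. It calls that missingness not at random, in which case the MAR mixed model is not guaranteed valid either.

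**Conclusion.** The conflict is real and stands in the current text of both documents. As written, the complete-case rule is the wrong one for these outcomes: it discards observed data, and it can be biased under the assumption that accompanies it.

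The size is uncertain. How many truncated participants are lost depends on the undefined visit slot, on accrual, and on whether an unscheduled visit counts as missing. That loss costs precision only. Bias needs outcome-related dropout and is modest in the assumed case where the mechanism is common to both arms. The 38% attenuation is not a forecast: it needs an arm-differential mechanism that no document states. The SDs, true difference and dropout model are all assumptions, so the simulation shows direction and rough scale.

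The primary time-to-event outcome is unaffected. This should be corrected, but it does not threaten the trial's main result.

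**What to change.** - In SAP 4.3 and 6.5.3, delete the complete-case wording for the longitudinal outcomes.
- State instead that every randomised participant with a baseline and at least one post-baseline value enters the mixed model in the allocated arm, with all observed visits, under MAR. A missed visit, truncated follow-up or early exit does not remove the visits already observed.
- Define which model visit the truncated Final Follow-up belongs to.
- Record the departure from Protocol 10.8 in SAP 6.8, or amend Protocol 10.8 to match. Otherwise the corrected SAP would contradict the protocol.

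The cost is wording only, since the mixed model is already planned. The resulting set is still a modified intention-to-treat set and should be labelled as such.
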